**TABLE 3– STUDY SCHEDULE**

	Screen Visit	Remote, Indep. SAFER Rater Only	V1 Baseline Visit	V 2	V 3	V 4	V 5	V 6	V 7	V 8	V 9	V 10	V 11
	Day -28 to Day -7		Day 0	Day 1	Day 2	Day 5 +/- 2 days	Day 8 +/- 2 days	Day 11 +/- 2 days	Day 14 +/- 2 days	Day 17 +/- 3 days	Day 21 +/- 3 days	Day 23 +/- 4 days	Day 28 +/- 4 days
Informed Consent	X												
Inclusion/Exclusion	X		X										
SCID-5	X												
SDQ	X		X	X	X	X	X	X	X	X	X	X	X
HAM-D17			X										
HAM-D6				X	X	X	X	X	X	X	X	X	X
MADRS	X	X*	X		X	X	X	X	X	X	X	X	X
CGI-S	X	X*	X	X	X	X	X	X	X	X	X	X	X
CGI-I			X	X	X	X	X	X	X	X	X	X	X
MGH ATRQ	X	X*											
Medical History	X												
Concomitant Medications	X		X	X	X	X	X	X	X	X	X	X	X
CHRT	X		X	X	X	X	X	X	X	X	X	X	X
Menopause and Hormonal Status (RLHQ) ††			X										
Vital Signs and AEs **	X		X	X	X	X	X	X	X	X	X	X	X
Physical Exam	X								X				X
12-lead ECG	X												
ECG			X			X	X	X	X		X		
Urine tox screen test	X		X										

Pregnancy test (urine)	X		X										
Chemistry, CBC **	X								X				X
TSH, HbA1c	X												
Randomization			X										
Intranasal ketamine administration			X			X	X	X	X		X		
Study Drug Dispensation			X				X		X		X		

\*Performed by MGH CTNI remote, independent rater. \*\*Refer to Table 4 for specific tests to be performed. ††Menopause and hormonal status questionnaire (RLHLQ, Modules 1 and 2 in all women, and Module 3 (Day 30) in premenopausal women only).

#### I.1.b. REMOTE INTERVIEW

To ensure that the appropriate patients are entered into the trial, remote diagnostic assessments (SAFER Interview), and baseline depression severity and treatment history assessments (MGH ATRQ, MADRS, and CGI-S) will be performed remotely by the independent MGH CTNI rater, and the patient will be contacted by telephone while they are off-site between the screen visit and the baseline visit, during which call the above assessments will be performed. Sites will be notified of the results within 24 hours of the interview.

#### I.1.c. RANDOMIZATION

For entry into the study and randomization, all eligibility criteria MUST be met (e.g., all inclusion criteria and no exclusion criteria). Patients who meet inclusion/exclusion criteria at the baseline visit (Day 0) will be randomized in a 1:1 fashion to either brexpiprazole plus intranasal ketamine treatment or placebo plus intranasal ketamine. All subjects will be followed for up to 28 days post randomization in order to examine the efficacy, safety, and tolerability of the study drug as well as the durability of the study drug's effects.

Specifically, patients will return for outcome assessments 24 hours after initiating treatment (Day 1), 48 hours after initiating treatment (Day 2), and then every 3 days after that for 26 days, with end of study visit one week after the last double-blind visit. (See Table 3 for the Study Schedule of the events.)

Patients with a MADRS score below 20 at either the screening or baseline visits will be excluded from further participation in the study. Upon determining at the baseline visit (Day 0) that a patient still meets all entry criteria for the study, the patient will be assigned (by study subject number assigned at consent) to the next randomization slot from the randomization list that will have been generated by the MGH Biostatistician.

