## G. STUDY DESIGN

### G.1. OVERVIEW

This is a multi-site, double-blind, placebo-controlled study of the acute efficacy of oral brexpiprazole or placebo combined with intranasal ketamine added to ongoing, stable, and adequate antidepressant therapy (ADT) in the treatment of adults with MDD with TRD. Adequate ADT is defined as a therapeutically sufficient dose for a sufficient treatment period, which would be expected to be effective as listed in the MGH ATRQ.

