**TABLE 2– OVERVIEW OF STUDY SCHEDULE**

Screen Visit	Screening Period	V1 / Baseline Visit	V2	V3	V4	V5	V6	V7	V8	V9	V10	V11
Day -28 to Day -7	Taper (opt.) 5 half-lives of excluded psychotropic drug(s)	Day 0	Day 1	Day 2	Day 5	Day 8	Day 11	Day 14	Day 17	Day 21	Day 23	Day 28
		Baseline Assess.	Assess.	Assess.	Assess.	Assess.	Assess.	Assess.	Assess.	Assess.	Assess.	Assess.
		Intranasal Ketamine Admin.	Assess.	Assess.	Intranasal Ketamine Admin.	Intranasal Ketamine Admin.	Intranasal Ketamine Admin.	Intranasal Ketamine Admin.	Assess.	Intranasal Ketamine Admin.	Assess.	Assess.
		Study Drug*	Study Drug*	Study Drug*	Study Drug*	Study Drug*	Study Drug*	Study Drug*	Study Drug*	Study Drug*	Study Drug*	Study Drug*

\*Brexipiprazole or Placebo

Subjects will be screened for eligibility as detailed above. Study participants will be consented prior to the administration of any procedure or wash-out. Following a washout period, under the close supervision and monitoring of the study clinicians, for patients on psychotropic drugs (with the exception of ongoing antidepressant therapy and of ongoing hypnotic therapy), baseline assessment, MGH CTNI remote interview, and re-confirmation that all criteria for entry into the study are met, eligible subjects will be randomly assigned to one of two arms: brexpiprazole plus intranasal ketamine (n=25) or placebo plus intranasal ketamine (n=25). The brexpiprazole dose will be titrated in the following manner: 0.5 mg/day during the first week, at the Visit 5/Day 8 visit, the dose will be increased to 1 mg/day, at Visit 7/Day 14 the dose will be increased to 2 mg/day, and at Visit 9/Day 21, the dose will be increased to 3 mg/day. If the dose escalation is not tolerated, patient can go back to previous dose (fixed-flexible dose escalation). As per Table 2, all subjects will be followed for 28 days to examine the efficacy and tolerability of brexpiprazole plus intranasal ketamine’s effects. The study assessments will be performed at Days 0, 1, 2, 5, 8, 11, 14, 17, 21, 23, and 28 to assess the safety and efficacy of brexpiprazole plus intranasal ketamine compared to placebo plus intranasal ketamine treatment therapy in depressed patients who have demonstrated an inadequate response

to at least 2 adequate antidepressant therapies (ADTs) during the current MDE. Intranasal ketamine (40 mg) will be administered after all the assessments are completed on Days 0, 5, 8, 11, 14, and 21.

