## N. DATA ANALYSIS

To analyze the primary outcome data, we will use a linear mixed model for the observations taken at baseline, and subsequent visits, with terms for visit, and visit\*treatment for visits other than baseline, the primary contrast of interest being the difference between the two weeks (Day 14) value for active treatment and placebo. To address missing data, we will use all available data and use a restricted maximum likelihood estimation procedure, as implemented by SAS Proc MIXED. The model will include a site, a site\*time effect and a site\*time\*treatment interaction. The latter will be removed if not significant. Number of comorbid medical and psychiatric disorders and duration of illness, as measured prior to randomization, will be included as covariates. For the continuous secondary efficacy variables, the same approach as for the primary efficacy variable will be used for the analysis.

Power analysis: the sample size was chosen to ensure 80% power to detect an effect size of 0.8 on the SDQ between brexpiprazole plus intranasal ketamine treatment and placebo at a two-sided 0.05 significance level. This assumes the randomization of 52 subjects (26 subjects per arm).

O. PROTOCOL SIGNATURE PAGE

I have read this protocol and agree to adhere to the requirements. I will provide copies of this protocol and all pertinent information to the study personnel under my supervision. I will discuss this material with them and ensure they are fully informed regarding the conduct of the study according to 21 CFR parts 50, 54, 56 and 812, 45 CFR 46, to GCP as described in ICH guideline E6 and to hospital Institutional Review Boards.

\_\_\_\_\_  
Clinical Site

\_\_\_\_\_  
Principal Investigator Signature

\_\_\_\_\_  
Date

\_\_\_\_\_  
Principal Investigator  
Printed Name

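### The primary model adjusts for site, but no stratification or blocking by site is described; a list blocked within site is a cheap improvement, with a gain that depends on the number of sites

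*Combined protocol and SAP*

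**What the plan says.** Section G.1 describes the trial in these words: "This is a multi-site, double-blind, placebo-controlled study". The number of sites and the expected enrolment per site are not given.

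Section I.1.c gives the only account of how allocation is made: 1:1, with each patient taking the "next randomization slot from the randomization list", which the biostatistician produces. Sections J.2 and J.7 refer to a randomization scheme and schedule but add no strata, block sizes or site-specific lists.

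Section N states "The model will include a site" and adds site-by-time and site-by-time-by-treatment effects, the last to be dropped if not significant. It does not say whether site is fixed or random.

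On power, Section N says "the sample size was chosen to ensure 80% power to detect an effect size of 0.8 on the SDQ" at a "two-sided 0.05 significance level", and "This assumes the randomization of 52 subjects (26 subjects per arm". No allowance is made for adjustment by site.

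**The concern.** The analysis conditions on a factor that the randomization, as described, is not said to balance. With 52 patients spread over several sites on one list, the arms will be uneven within sites by chance. In a model with fixed site effects, only within-site comparisons inform the treatment contrast, so uneven sites lose information. A site that holds a single arm adds nothing to that contrast and cannot support its part of the three-way interaction.

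The power statement is the balanced two-sample figure and has little slack. Section N makes no dropout allowance, and Section J.6.a says that patients who discontinue are not replaced. What is at stake is precision, not bias or the type I error rate.

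**Working it through.** **Inputs from Section N:** effect size 0.8, two-sided 0.05, 26 per arm, N = 52. **Assumed:** S = 2, 3, 4, 6 or 8 sites of nearly equal size; site fixed; no true between-site variance; a single-time-point comparison at Day 14. The overview in Section I.1 gives 25 per arm instead of 26. That is a separate inconsistency, and 26 is used here.

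**Step 1, the plan's own figure.** Treatment information is the sum of squares of the treatment indicator, 52 × ½ × ½ = 13. The noncentrality is 0.8 × √13 = 2.884. With 50 degrees of freedom the noncentral t gives power **80.7%**, so the stated 80% reproduces.

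**Step 2, degrees of freedom alone.** With perfect balance within 8 sites, the noncentrality stays at 2.884 and the degrees of freedom fall to 52 − 8 − 1 = 43. Power is 80.5%. Estimating the site effects costs almost nothing in itself.

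**Step 3, one list, 26/26 overall, no site strata.** The expected information left after removing site means is 13 × [1 − (S − 1)/51]. The noncentrality at that value is 0.8 times its square root, with 52 − S − 1 degrees of freedom. The power columns average over simulated allocations.

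| Sites | Expected information | Noncentrality | Power, one list | Power, blocks of 4 within site |
|---|---|---|---|---|
| 2 | 12.75 | 2.856 | 79.9% | 80.6% |
| 3 | 12.49 | 2.827 | 79.1% | 80.5% |
| 4 | 12.24 | 2.798 | 78.2% | 80.4% |
| 6 | 11.73 | 2.739 | 76.3% | 80.2% |
| 8 | 11.22 | 2.679 | 74.4% | 79.4% |

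Example for 6 sites: 13 × (1 − 5/51) = 11.73, and 0.8 × √11.73 = 2.739. A single list blocked centrally in fours gives the same figures to within 0.1 point, so central blocking is no remedy. Pure coin-flip allocation gives 77.4%, 75.5% and 73.5% for 4, 6 and 8 sites.

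**Step 4, sensitivity to the site assumptions.**
- *Fixed site, site explaining 5% / 10% of total variance* (0.8 defined on the total SD; one list): 80.2% / 82.3% with 4 sites, 78.4% / 80.5% with 6, and 76.4% / 78.6% with 8.
- *Random site intercept* (variance ratio treated as known, site variance 0-10%, coin-flip allocation): 79.9-82.6% for 4-8 sites.

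**Step 5, one-arm sites.** With 8 equal sites, one list leaves some site with a single arm in about 12% of allocations; blocks of 4 within site leave none. Uneven enrolment changes this. Under assumed unequal site sizes, the chance of at least one such site falls from 56% to 33% with 6 sites and from 82% to 56% with 8. The reason is simple: a site with one patient always holds one arm, and two patients from a block of 4 share an arm with probability 1/3 (against 1/2 for a coin flip).

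**Step 6, skewed enrolment.** Blocks of 4 within site then give 80.3% with 4 sites, 79.7% with 6, 78.1% with 8 and 76.1% with 10.

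**The case against.** The case against has real weight.

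- **The text is silent.** A reader might infer that the plan declares an unstratified list. It does not. A list with a section for each site would fit the same wording, and Sections J.2 and J.7 do not rule that out. This objection stands: the single list is a reading, although it is the natural one.
- **The site count is unknown.** A reader might conclude that the trial's power is 74-78%. That range needs about 4-8 sites; with 2 or 3 the loss is only 1-2 points. This also stands.
- **Site may be random, or may explain some variance.** Section N specifies a mixed model without saying which. Step 4 shows the shortfall from 80% then shrinks or disappears. This stands for the size of the loss. Even so, at the same site variance with site fixed, blocking within site still does better: for example, 82.2% against 78.4% with 6 sites and 5% site variance.
- **The calculation is not the planned analysis.** Section N models baseline as an outcome, so the contrast is baseline-adjusted. If 0.8 refers to the SD of change, adjustment multiplies the variance by (1 + r)/2, where r is the baseline to Day 14 correlation. For an assumed r of 0.3 to 0.7, one list gives 92-84% with 4 sites, 91-83% with 6 and 90-81% with 8. If 0.8 already reflects adjustment, there is no such gain. The documents do not say which, so a fall below 80% is not established.
- **Blocking does not cure one-arm sites.** This is correct, as Step 5 shows, and it is why pooling belongs in the fix. The three-way term is also dropped if not significant, which limits the harm.

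**Conclusion.** The point holds as a cheap improvement. Section I.1.c describes no balancing by site, while Section N adjusts for it. Run as one list, with site fixed and little between-site variance, the design gives about 79-80% power with 2-3 sites, 78% with 4, 76% with 6 and 74% with 8, against 80.7% under balance. The loss comes from imbalance within sites, not from degrees of freedom.

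These figures rest on assumed site counts, similar site sizes and a single-time-point comparison. The shortfall is small or absent with a random site effect, and is offset partly or fully when site explains 5-10% of the variance. It would be wrong to infer that the trial is shown to be underpowered or its result invalid. Randomization on one list still gives a valid comparison; only efficiency is affected.

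**What to change.** In Section I.1.c, state that the list is generated separately for each site in permuted blocks of varied size, with block sizes concealed from the sites, and that each site draws from its own list. If the list is already built this way, one clarifying sentence is enough.

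In Section N, keep site as the stratification factor, give the number of sites, say whether site is fixed or random, and pre-specify how very small sites are pooled. The pooling rule should be set without sight of treatment codes.

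With 2-8 sites of similar size this restores about 79-81% power under the Step 3 assumptions, and somewhat less with many very small sites. It adds no patients, visits or procedures: the biostatistician already produces the list, and the site pharmacists already pack to the scheme (Section J.2). The downside is slight predictability from blocking, limited by varied and concealed block sizes. The change has to be made before the first patient is randomized.

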#### I.1.d. BASELINE VISIT (VISIT 1) (DAY 0)

The patient should be instructed to refrain from eating and avoid alcohol as well as opioid and narcotic analgesics the day of the baseline visit (after midnight), as well as benzodiazepines within 2 hours of the intranasal administration. For visits in the afternoon, patients may have a light meal in the morning no less than 3 hours before the study visit.

Upon arrival, the patient will be administered the SDQ, the 17-item Hamilton Rating for Depression (HAM-D-17), the MADRS, the CGI-I, the CGI-S, and the CHRT by the site rater.

Upon completion of all study-related inclusion procedures as listed in Table 3 and upon the investigator's confirmation that the patient still meets all of the study inclusion criteria and none of the exclusion criteria, the patient may be randomized.

All subjects will be dispensed brexpiprazole or placebo, as well as 40 mg of ketamine administered intranasally. The study drug ( brexpiprazole or placebo) should be taken by the patient before ketamine administration. Detailed instructions for ketamine dose preparation will be provided to the pharmacist in an additional guidance document. Storage conditions should be followed according to the package insert. Dosing procedures will be provided to the clinical unit in a separate document.

Physiological Monitoring: Medical staff monitoring the ketamine administration will be prepared to treat increases in blood pressure greater than 180/110 mm Hg or heart rate greater than 110 bpm, or follow their institutional guidelines if more conservative. If these elevations resolve spontaneously within a short time period, they will generally not be treated. Heart rate and blood pressure should be recorded at 15 minutes post dose, 30 minutes post dose, 45 minutes post dose, 1 hour post dose, 90 minutes post dose and 2 hours post dose. The ketamine intranasal administration will be discontinued in the event that three consecutive measurements remain above protocol-defined limits, or according to institutional guidelines if more conservative, despite antihypertensive administration. A study psychiatrist will release the subject at the conclusion of the testing period at the end of the visit. A trained research assistant along with a research nurse will be present during the entire administration and monitoring period. All side effects will be recorded during the ketamine treatment and for the 2 hours following. Clinically relevant vital sign changes will be recorded as adverse events.

A study physician (MD or DO) will be present in the unit throughout the administration of ketamine so that potential adverse events can be evaluated and treated promptly, and will assess the patient for AEs, both physical and psychiatric, at Hours 1 and 2 following completion of the ketamine administration. They will remain available in the study site until discharge. The study physician will have a current certificate for ACLS training. An emergency medical cart will be available with oxygen delivery capability. The study physician will remain in the unit for at least one hour following the termination of the ketamine treatment or until the patient meets Aldrete criteria (good respiration, O2 saturation, consciousness, circulation, and activity) for Phase 2 post-anesthesia care, whichever

period is longer. For sites which are not hospital-based, procedures for emergency transfer to the Emergency Department will be described in the Manual of Operations (MOP).

Discharge Procedure: Discharge procedures should not begin earlier than 3 hours following completion of the intranasal administration of ketamine. Before being discharged patients should be awake and alert, feeling well, with no nausea, vertigo, or dizziness. There should be no significant change in vital signs from prior to ketamine administration.

They will be given a small meal before discharge.

Patients will be instructed not to drive. The study coordinator will release them to the care of an adult escort, who will accompany the patient home.

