### J.5. CONCOMITANT THERAPY

All concomitant medications taken during the study will be recorded in the Concomitant Medication Log for each patient, along with dosage information and start and stop dates. Allowed concomitant medications include any prescription or over-the-counter medication not specifically excluded by the protocol (see Appendix 1), as well as stable, ongoing antidepressant therapy and stable allowed hypnotic therapy. Patients requiring excluded drugs will be discontinued from the study.

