## APPENDIX 1 CONCOMITANT MEDICATIONS

Medications Allowed (Y) and Not Allowed (N) as Concomitant Medications

Drug Name or Class	Episodic Use (PRN)	Chronic Use	Restrictions/Comments
Analgesics	Y	Y	Nonnarcotic analgesics are allowed. Medically appropriate episodic use of narcotic analgesics is allowed for acute medical indications but is limited to no more than 3 days for each episode, and may not be taken the day of the ketamine administration starting at midnight. Chronic NSAID use is exclusionary; tramadol is also not allowed.
Anesthetics, general	Y (except for ketamine, which is excluded)	—	If procedures requiring general anesthesia are to occur/have occurred, please contact MGH CTNI to report the medical condition(s).
Anesthetics, local	Y	N	—
Anorexics	N	N	—
Antacids	Y	Y	—
Antiacne	Y	Y	Topical agents only, including topical antibiotics. Isotretinoin (Accutane) is not allowed.
Antianginal agents	N	N	—
Antiarrhythmics	N	N	Amiodarone is excluded
Antiasthma agents	Y	Y	—
Antibiotics	Y	Y	Chronic use of topical antibiotics for acne is allowed, with the exception of the MAOI linezolid (Zyvox) and isoniazid, which are not allowed. Erythromycin, clarithromycin, rifampin are excluded.
Anticoagulants	N	N	Warfarin (Coumadin) is not allowed. Antiplatelet agents are allowed (see "Antiplatelets").

Drug Name or Class	Episodic Use (PRN)	Chronic Use	Restrictions/Comments
Anticholinergics	Y	Y	Except for scopolamine.
Anticonvulsants	N	Y	Gabapentin, and pregabalin are allowed. Other anticonvulsants are not allowed, including lamotrigine and carbamazepine.  Stable in dosing at least four weeks prior to randomization is required.
Antidepressants	N	Y	Stable (for at least 4 weeks prior to screening), ongoing antidepressant therapy is required during the course of the study. No dose changes are allowed during the study. Monoamine oxidase inhibitors (which may have unknown drug-drug interactions) are excluded. Concomitant use of trazodone (up to 200mg daily) is allowed. Nefazodone is excluded.
Antidiarrheal preparations	Y	N	Only loperamide HCl (Imodium), bismuth subsalicylate (Pepto-Bismol), and kaolin preparations are allowed.
Antifungals, systemic	N	Y	—
Antifungals, topical	Y	Y	Ketoconazole and itraconazole are excluded

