Antihistamines	Y	Y	The use of combinations containing pseudoephedrine or phenylephrine is not allowed. Combination products containing the word nighttime or are specifically marketed for before sleep routinely include an antihistamine and are not allowed. Combination products ending in “-D” routinely contain a stimulant such as phenylephrine, and the appropriate limits above apply to them. (See “Cough and Cold Preparations” for combination products.)

Drug Name or Class	Episodic Use (PRN)	Chronic Use	Restrictions/Comments
Antihypertensives	N	Y	Diltiazem, verapamil are excluded
Anti-impotence medications	Y	Y	—
Anti-inflammatory drugs	Y	Y a	Indomethacin (Indocin) and systemic corticosteroids are not allowed. Chronic NSAID use is exclusionary.
Antifungal	Y	Y	Itraconazole is excluded
Antimigraine	N	N	Triptans are not allowed
Antinauseants/Antiemetics	Y	N	Phosphoric acid preparations (Emetrol, Emecheck), bismuth subsalicylate (Pepto-Bismol), cola syrup, 5-HT 3 receptor antagonists (e.g., ondansetron), and prokinetic agents (metoclopramide) are allowed. Scopolamine is not allowed (see section on antihistamines).
Antineoplastics/ Immunosuppressant agents	N	Y c	Interferons, methotrexate, and other immunosuppressant agents are not allowed. Call MGH CTNI for approval for certain cases in cancer remission maintaining therapy.

Drug Name or Class	Episodic Use (PRN)	Chronic Use	Restrictions/Comments
Antiobesity/Appetite suppressants	N	N	OTC Alli (Xenical), sibutramine (Meridia), and phentermine (Adipex-P and others) are not allowed.
Antiplatelet agents	N	Y b	Aspirin (maximum 325 mg/day) and clopidogrel (Plavix) are allowed. Note that use of an SSRI or of a triple uptake inhibitor may increase bleeding times and possibly prothrombin times.
Antipsoriatic treatments	Y	Y	Only topical agents are allowed. Acitretin (Soriatane) is not allowed.
Antipsychotics	N	N	
Antismoking medications	N	Y c	Varenicline (Chantix) is not allowed. Chronic nicotine replacement may be allowed in certain cases after review with MGH CTNI.

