Hormones: reproductive	N	Y	Systemic hormonal contraceptives (oral contraceptives of estrogen and progestin combinations, depot injections such as Depo-Provera, the contraceptive implant Implanon, or transdermally delivered contraceptives such as Ortho Evra) are allowed
Hormones: thyroid	N	Y	Thyroid hormone replacement is allowed (dosage of thyroid medication should be stable for 3 months before screening). Therapeutic use for psychiatric disorders (e.g., T3 augmentation) is not allowed
Hypoglycemic agents	N	Y	Oral hypoglycemic agents are allowed. Insulin is not allowed
Hypolipidemics	N	Y b	Ezetimibe (Zetia) is allowed
Hypolipidemics: bile acid sequestrants	N	N	—
Hypolipidemics: fibrates	N	Y b	Gemfibrozil and fenofibrate are allowed
Hypolipidemics: niacin	N	N	Niacin and niacinamide are not allowed
Hypolipidemics: statins	N	Y b	Lovastatin, simvastatin, pravastatin, atorvastatin, fluvastatin, and rosuvastatin are allowed
Laxatives	Y	Y a	Only fiber-based products and docusate sodium (Colace) are allowed
Lithium	N	Y	Stable in dosing at least four weeks prior to randomization is allowed.
Medications that are primarily metabolized by CYP2C8 (e.g., cerivastatin, paclitaxel, repaglinide, sorafenib, and toremide)	N	N	—
Muscle relaxants	N	N	—
NMDA receptor antagonist	N	N	Memantine is excluded.

Drug Name or Class	Episodic Use (PRN)	Chronic Use	Restrictions/Comments
Opioid agonists/analgesics (e.g., codeine, hydrocodone, methadone, morphine, maperidine, propoxyphene) and antagonists (e.g., naltrexone, naloxone, nalmeffene)	N*	N*	See section on analgesics for exceptions
Proton pump inhibitors or H2 receptor blockers	Y	Y	Cimetidine
Sedatives/hypnotics	N	Y	Ongoing, stable hypnotic therapy (e.g., zolpidem, zaleplon, benzodiazepine hypnotics, and low-dose trazodone 50-200mg) will be allowed during the course of the study. Eszopiclone is not allowed. Patients should not take benzodiazepines, within 2 hours of ketamine administration.
Steroids/systemic	Y	N	Systemic steroid treatment will be allowed only for medical emergencies, such as severe allergic reactions
Steroids/topical and inhalant	Y	Y	—
Steroids/intra-articular	Y	NA	—
Stimulants	N	N	Oral or transdermal methylphenidate, amphetamine products or prodrugs, pseudoephedrine, modafinil (Provigil), and other medications of same category are not allowed
Vaccines	Y	NA	—

Drug Name or Class	Episodic Use (PRN)	Chronic Use	Restrictions/Comments

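### Appendix 1 and J.5, read literally, remove from the study a patient given the antihypertensive rescue that I.1.d foresees after ketamine

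*Combined protocol and SAP*

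**What the plan says.** **Physiological monitoring (I.1.d).** Medical staff are to be "prepared to treat increases in blood pressure greater than 180/110 mm Hg or heart rate greater than 110 bpm", or to follow institutional guidelines where those are more conservative. Treatment is not automatic: "If these elevations resolve spontaneously within a short time period, they will generally not be treated". Ketamine is discontinued when three consecutive measurements stay above the limits "despite antihypertensive administration", or earlier under more conservative institutional guidelines. Later ketamine visits refer back to this procedure and to the Manual of Operations.

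**Concomitant medication (Appendix 1).** The columns are episodic (PRN) use, chronic use and comments. The relevant row reads "Antihypertensives N Y Diltiazem, verapamil are excluded". So episodic use is not allowed, chronic use is allowed, and two agents are named as excluded. None of the table's footnotes is attached to the row.

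**Consequence (J.5).** J.5 uses Appendix 1 to define what is excluded and then says: "Patients requiring excluded drugs will be discontinued from the study". It gives no exception. J.6.a.1 adds that patients who discontinue are not replaced.

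**The concern.** The three provisions do not fit together. I.1.d foresees a short course of antihypertensive treatment and, by inference, lets a patient who responds carry on. J.5, applied as written to the Appendix 1 row, takes the same patient out of the study. Nothing in the two documents' text says which provision governs, so two sites could handle the same event differently.

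What is at stake is the retention of that patient and the SDQ record. Ketamine is given after each visit's assessments are complete. Removal after the Day 0, 5, 8 or 11 dose may therefore cost the Day 14 SDQ, which is the primary contrast in section N. Removal after the Day 14 or 21 dose may cost the Day 28 SDQ, which is a secondary aim.

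**Working it through.** **1. Does the text conflict?**

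| Question | Where | Answer |
|---|---|---|
| Is antihypertensive rescue foreseen? | I.1.d | Yes, above 180/110 mm Hg or 110 bpm, unless the rise resolves spontaneously |
| Does rescue alone stop ketamine? | I.1.d | No. Persistent elevation despite treatment, or stricter institutional rules, does |
| Is an episodic antihypertensive allowed? | Appendix 1 | No |
| Is there an acute-use exception in that row? | Appendix 1 | No |
| What follows from needing an excluded drug? | J.5 | Discontinuation from the study |
| Is the patient replaced? | J.6.a.1 | No |

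The same table does write out acute-use exceptions elsewhere. It allows narcotic analgesics for short acute indications and systemic steroids for medical emergencies. Their absence from the antihypertensive row can therefore be read as deliberate.

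**2. Which SDQ could be lost?** Table 3 gives the Day 14 visit a window of ±2 days, so Days 12 to 16. The early-termination visit (I.1.o) follows the Day 28 procedures, which include the SDQ.

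- The Day 11 visit may fall on Days 9 to 13. A prompt early-termination visit after that dose can land inside Days 12 to 16, so a Day 14 value may survive.
- The Day 8 visit may fall as late as Day 10. A prompt early-termination visit after the Day 0, 5 or 8 dose would usually come before Day 12.
- The documents give no timing for the early-termination visit, so loss is possible but not certain.

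**3. How much power is involved?** First, the plan's own figure. The inputs from section N are effect size d = 0.8, two-sided alpha 0.05 and 26 per arm. For a two-sample t-test the noncentrality is d / √(1/n₁ + 1/n₂) = 0.8 / √(1/26 + 1/26) = 2.884 on 50 degrees of freedom. Power is 80.7%, which agrees with the stated 80%.

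The documents give no rescue rate, so the counts below are assumptions. Two bounds are used:

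- **Complete-case.** A removed patient contributes nothing to the Day 14 contrast.
- **Mixed-model approximation.** If m patients leave an arm after Day 11, the variance of that arm's Day 14 mean is proportional to (1 − R²)/(26 − m) + R²/26. Here R² is the share of Day 14 variance explained by earlier visits, with an assumed range of 0 to 0.75. At R² = 0.75 and m = 1, the effective n is 1 / (0.25/25 + 0.75/26) = 25.74. At m = 2 it is 1 / (0.25/24 + 0.75/26) = 25.47.

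| Assumed removals | Share of 52 | Complete-case power | Power at R² = 0.75 |
|---|---|---|---|
| None | 0% | 80.7% | 80.7% |
| 1 | 1/52 = 1.9% | 79.9% (25 vs 26) | 80.5% |
| 2, one per arm | 2/52 = 3.8% | 79.1% (25 vs 25) | 80.3% |
| 2, same arm | 2/52 = 3.8% | 79.1% (24 vs 26) | 80.3% |

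The largest drop shown is 80.7 − 79.1 = 1.6 percentage points.

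**4. How likely is rescue?** Exclusion 17a screens out patients at or above 160 systolic or 100 diastolic. The 40 mg intranasal study cited in D.2.a, with 18 completers, reports no clinically significant hemodynamic changes. K.1.b reports no clinically significant vital-sign changes in the studies it summarises. All this points to a rare event, though there are six doses per patient at which it can arise.

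**The case against.** The strongest reply is that Appendix 1 was never meant to cover what the protocol itself directs. The general anesthetics row reads "Y (except for ketamine, which is excluded", and the table also has "Antipsychotics N N" and "NMDA receptor antagonist N N Memantine is excluded". Applied to the study drugs, J.5 would discontinue everyone on Day 0. On this view a specific instruction in I.1.d overrides a general list, and J.6, which asks for every effort to retain patients, supports that.

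Much of this stands as evidence of intent: rescue was probably meant to be exempt. It does not remove the conflict. A rescue antihypertensive is a concomitant medication to be logged under J.5, and the study drugs are not. J.6 lists acceptable reasons for discontinuation but exempts nothing from J.5. J.6.a.1 lets the physician stop treatment for an unacceptable pressure rise, but does not say what happens when the physician judges that the patient can continue.

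The reply also limits how far the point goes. A reader might infer any of the following, and the documents support none of them:

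- *Staff would hold back treatment.* I.1.d requires staff ready to treat, an ACLS-certified physician in the unit and an emergency cart. Nothing suggests hesitation.
- *Sites have no rule at all.* The Manual of Operations, which is not among the documents, holds the physiological monitoring procedures and may address rescue.
- *The Day 14 SDQ is lost.* The early-termination visit may supply it. I.5.b.1 and J.6.a.1 also ask for continued follow-up, although I.5.b.1 gives safety data as the purpose.
- *Power is materially damaged.* It is not, on the figures above.

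**Conclusion.** The point holds as an inconsistency in the protocol text. I.1.d foresees antihypertensive rescue without making it a stopping event, while Appendix 1 and J.5, read literally, remove the rescued patient without replacement. That the patient may continue after responding is an inference from the stopping rule and is not stated outright.

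The statistical size is negligible: at most 1.6 percentage points of power for two assumed removals, and less under the planned mixed model if earlier visits predict Day 14 well. Both the removal counts and R² are assumptions, because the documents give no rescue rate and no correlation between visits. The case for a change rests on consistent handling across sites and on keeping SDQ data from a patient treated as the protocol foresees. It is worth doing because it costs almost nothing. Confidence is medium, since the unseen manual may already settle the matter in practice.

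**What to change.** Add one sentence to J.5 and matching text in the Appendix 1 antihypertensive row. An antihypertensive other than diltiazem or verapamil, given on site by study staff under I.1.d for a post-ketamine rise in blood pressure or heart rate, is permitted, is recorded as a concomitant medication, and does not by itself require discontinuation from the study.

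Keep the exemption that narrow. I.1.d also has the physician assess psychiatric adverse events, so wording that covered any drug for a ketamine reaction would admit antipsychotics or unscheduled benzodiazepines, which could affect the SDQ while visits continue. It would also admit the two agents the row names as excluded. Leave the three-reading rule in I.1.d, the precedence of stricter institutional guidelines and the physician's discretion in J.6.a.1 as they are.

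The cost is one sentence and one table cell, with no added visits or procedures. The downside is that a few patients with a treated hypertensive reaction remain in the study, subject to those unchanged stopping rules.
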